We propose a prospective, randomized, double-blinded, placebo-controlled clinical trial on the use of perioperative intravenous lidocaine infusion in order to decrease pain scores and opioid consumption after robotic-assisted prostatectomy and robot assisted partial nephrectomy.

Patients undergoing urological robotic assisted surgery will be randomized 1:1 to receive either intraoperative 0.8% lidocaine or normal saline at 1 mg/kg/h for patients younger than 65 years and 0.5 mg/kg/h for patients greater than or equal to the age of 65 to be delivered by continuous infusion for 24 hours intra- and post-operatively. Opioid use will be monitored for up to 14 days post-operatively as well as pain scores.

OBJECTIVES AND SCIENTIFIC AIMS

Clinical Hypotheses:

Primary Hypothesis:

We hypothesize that use of perioperative lidocaine infusion for 24 hours in urology robotic surgeries would result in less pain and less opioid use compared to the placebo.

Exploratory Hypotheses:

We hypothesize that the use of the lidocaine infusion compared to placebo would:

1. result in less opioid consumption in first 24 hours and 14 days post-operatively
2. decrease length of stay in the PACU and improve SpO₂ levels in PACU
3. decrease postoperative nausea and vomiting
4. decrease time to first ambulation after the surgery
5. improve recovery of bowel movements after surgery
6. improve patient satisfaction levels after surgery
7. decrease length of stay in hospital

Therefore:

Primary Endpoint is:

- Difference in post-operative pain

Secondary Endpoints are:

- Difference in opioid consumption in first 24 hours, discharge and 14 days post-operatively (utilizing morphine equivalents)
- Difference in length of hospital stay determined by surgeon excluding social factors that may delay discharge (discharge readiness; hours)
- Difference in post-operative ileus duration (hours)
- Difference in time in the Post Anesthesia Care Unit (PACU) after surgery (discharge readiness and actual discharge; minutes)
- Difference in return of flatus after surgery (hours)
- Difference in time to out of bed to chair after surgery (hours)
- Difference in time to first ambulation in the hallway after surgery (hours)

BACKGROUND AND STUDY DESIGN/INTERVENTION

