Surgical complications will be assessed prospectively and retrospectively and reviewed using the institutional standard for complications reporting for all surgical patients as followed by the Department of Surgery. Standardized graded complications and adverse effects at UM utilize the five-point modified Clavien-Dindo system. Grade I include complications requiring monitoring but no intervention; Grade II requires bedside or medical treatment; Grade III constitute adverse events requiring surgical or procedural intervention with return to normal functioning; Grade IV includes disabling, life-threatening complications with resulting functional loss and grade V is death of the patient. This is a modification of the Clavien-Dindo system for reporting complications with defined, categorized and classified events that will be segregated into time periods of ≤ 30 days, 31-90 days and > 90 days after surgery and includes medication complications following NCI CTCAE version 5 guidelines.

CRITERIA FOR THERAPEUTIC RESPONSE/OUTCOME ASSESSMENT

If the surgery is aborted for any reason before attempted excision of the mass or intravenous infusion fails for any reason, the patient will be removed from the study and replaced. Based on past experience these issues are rare events. If a partial nephrectomy converts to radical nephrectomy, infusion will be continued and the data will be collected. If any robotic procedure converts to an open procedure, the subject will be excluded from the study. Lidocaine infusion will be continued or started (if subject is receiving normal saline) per surgeon request.

The intraoperative period is defined as the period from anesthesia induction to the extubation of the trachea. The surgical time is determined from the incision to the final skin closure.

The postoperative period is defined as the period from the extubation to the study endpoint at 14 days \pm 7 days.

Blood loss is defined as the estimate accounted from the suction device and absorptive sponges during the procedure, as described and agreed upon by the surgeon, anesthesiologist, circulating nurse, and surgical technician as covered by institutional guidelines.

Post-operative pain will be defined by the patient through the use of a 10 cm visual analog scale (VAS) and 11 point numeric scale (0-10).

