Length of hospital stay will be defined as the time the subject leaves the OR until subject meets standardized discharge criteria according to the surgeons' protocol, which will exclude social factors delaying real discharge times.

Post-operative ileus duration is defined as return of bowel function in hours from extubation per patients recall following nursing inquiry. Documentation will be done per standard of care by the nurse caring for study patient.

Flatus return is defined as return of flatus in hours from extubation per patients recall following nursing inquiry. Documentation will be done by nurse caring for patient following standard of care.

Patient satisfaction will be assessed 24 hours post-operative by Post Anesthesia Patient Satisfaction Assessment by research staff.

CRITERIA FOR REMOVAL FROM STUDY

Patients will be withdrawn from the study if they express a desire to do so, if it is determined to be in the patient's best interest to do so, or if they do not undergo initiation of their surgical procedure as stipulated previously. If lidocaine infusion is stopped subject will be excluded from analysis. If surgery is converted from robotic assisted to open the subject will be excluded from analysis. Patients who are not evaluable for the study primary endpoint by failure to obtain

data for the primary endpoint will be excluded from the study and further analysis will not be performed.

BIOSTATISTICS

Sample Size

The primary outcome for the study is the patient's pain score at discharge. Although additional analyses are planned, the sample size estimate is based on this outcome. Assuming a common standard deviation of two-points, a sample size of 40 with 20 per treatment arm will provide 80% power to detect a 2-point difference between groups when testing a two-sided alternative at the 5% level of significance using Wilcoxon Rank Sum Test. To take into account the loss to follow up, the drop-out inflated enrollment will be 46 subject with 23 subjects in each group assuming the same power.

Unadjusted and Adjusted Analysis

The unadjusted analysis will be designated as primary analysis and it will be performed to assess the pain level difference between the two groups. The adjusted analysis which will be designated as secondary analysis will incorporate other covariates like type of surgery in addition to the treatment assignments as covariate.

Proposed Analyses

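### Patients are dropped, and some replaced, for events after randomisation, including infusion stops for lidocaine-toxicity symptoms, and no as-randomised analysis is planned

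*Combined protocol and SAP*

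**What the plan says.** The Design section randomises patients after written consent and starts the infusion 15 minutes after intubation. Every rule below therefore acts after randomisation.

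- **Infusion stopped.** Intervention stops the infusion for a list of symptoms (tinnitus, confusion and seizures among them) and takes the patient off study. Criteria for Removal from Study adds: "If lidocaine infusion is stopped subject will be excluded from analysis".
- **Infusion failed or surgery aborted.** Criteria for Therapeutic Response/Outcome Assessment says that if the "intravenous infusion fails for any reason, the patient will be removed from the study and replaced". The same sentence covers surgery aborted before excision is attempted.
- **Conversion to open.** The same section says "If any robotic procedure converts to an open procedure, the subject will be excluded from the study", followed by "Lidocaine infusion will be continued or started (if subject is receiving normal saline) per surgeon request". Criteria for Removal repeats the exclusion: "If surgery is converted from robotic assisted to open the subject will be excluded from analysis".
- **Missing primary data.** Patients without "data for the primary endpoint will be excluded from the study and further analysis will not be performed".

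The primary endpoint itself is stated in two ways. Objectives gives "Difference in post-operative pain", while Sample Size gives "pain score at discharge. Although additional analyses are planned, the sample size estimate is based on this outcome".

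The Biostatistics section names an unadjusted primary analysis, an adjusted secondary analysis, a Wilcoxon rank sum test and a GEE model. It defines no as-randomised set, no missing-data method and no sensitivity analysis for excluded patients.

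**The concern.** Randomisation protects a comparison only while patients stay in the group to which they were assigned. The stopped-infusion rule is the main problem. Its triggers are the symptoms that Toxicities/Side Effects associates with plasma lidocaine above 5 µg/mL, so the chance of exclusion can differ by arm because of the drug. If the patients who stop also differ in pain, the remaining groups are no longer comparable.

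The wording adds to this. Both passages on stopping refer to the lidocaine infusion and do not say whether a stopped saline infusion also leads to exclusion. Read literally, the rule could apply to one arm only. A failed infusion leads to replacement and a stopped one to exclusion, although the two events can overlap.

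The plan does not say whether pain scores are still collected after removal. If they are not, the as-randomised comparison could not be rebuilt later.

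The other rules matter less. Aborts and conversions are decided by blinded staff, have no documented link to arm, and mainly cost precision. The missing-data rule depends on the endpoint. If it is pain at discharge, a patient lacking only that score loses all further analysis despite the earlier VAS scores. If it is post-operative pain generally, only patients with no pain data are lost.

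**Working it through.** **Inputs from the plan.** SD 2, difference 2, two-sided 5%, Wilcoxon test, 20 per arm for 80% power, 10% dropout, 23 per arm enrolled (Sample Size; Table 2). Exclusion rates are not given and are assumed below.

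**The plan's sample size reproduces.** A two-sample t-test needs 16.7, so 17 per arm. Dividing by 0.864, the minimum relative efficiency of the Wilcoxon test (my assumption about the method), gives 17/0.864 = 19.7, so 20. Dropout: 20/0.9 = 22.2, so 23. For 90% power: 23/0.864 = 26.6, so 27, and 27/0.9 = 30. The sample size is not at fault.

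**Bias with no true effect.** Suppose the k of n lidocaine patients ranked highest on an exclusion score are dropped, no placebo patient is dropped, and the score has correlation r with pain. Then

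bias = −r × SD × m × k/(n − k),

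where m is the expected mean of the k largest of n standard normal values. For n = 23 and k = 3, m = 1.54:

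- r = 1: 2 × 1.54 × 3/20 = 0.46 points
- r = 0.5: 0.23 points
- r = 0.3: 0.14 points

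The sign reverses if r is negative. Simulation (100,000 trials per case, normal scores, Wilcoxon) agrees and adds the type I error:

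| Per arm | Excluded, lidocaine v placebo | Correlation with pain | Bias (points) | Type I error |
|---|---|---|---|---|
| 23 | 3 v 0 | 0 | 0 | 4.9% |
| 23 | 3 v 0 | ±0.3 | 0.14 | 5.5–5.7% |
| 23 | 3 v 0 | ±0.5 | 0.23–0.24 | 6.7% |
| 23 | 3 v 0 | ±1 (extreme) | 0.46 | about 12% |
| 23 | 1 v 0 | ±0.5 | 0.09 | 5.2–5.4% |
| 23 | 1 v 0 | ±1 (extreme) | 0.17–0.18 | 6.1% |
| 23 | 3 v 1 | ±0.5 | 0.14 | 6.0% |
| 20 | 3 v 0 | ±0.5 | 0.26 | 6.7–6.8% |
| 20 | 3 v 0 | ±1 (extreme) | 0.52 | about 13% |

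A second model gives the same picture. If a share of the lidocaine arm is excluded and has excess pain, bias = −share × excess. At 10% and 2 points this is −0.2 points; at 20% and 3 points, −0.6 points. Type I error is about 6% and 12% respectively, while analysing the same data as randomised stays near 5%.

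Equal losses unrelated to pain give no bias. Losing three per arm from 23 lowers power from 90% to 85%.

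**Power when stopped patients are kept.** True effect 2; stopped lidocaine patients are assumed to lose all benefit; a crossover is a placebo patient who gains the full effect.

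| Analysed per arm | None stopped | 1 stopped | 3 stopped | 3 stopped and 1 crossover |
|---|---|---|---|---|
| 23 | 90% | 87% | 79% | 75% |
| 20 | 85% | 81% | 70% | 65% |

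The diluted mean difference at 23 per arm with three stopped is 2 × 20/23 = 1.74 points. Excluding three lidocaine patients at random instead leaves 87% (20 v 23) or 82% (17 v 20).

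**The case against.** The textual reading is not in dispute; the case against is about size.

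- **Expected rates are low.** The protocol calls toxic levels unlikely and failed infusions or aborted surgery rare. Three exclusions against none is 3/23 = 13% of one arm. With one exclusion, type I error at correlation 0.5 is only 5.2–5.4%, and the 12% figure needs exclusion ranked perfectly by pain. Nothing in the documents links toxicity symptoms to discharge pain. This stands: the bias may well be small.
- **Arm dependence is blurred.** Symptoms are judged by blinded staff, both arms receive lidocaine at induction and local bupivacaine at closure, and saline may be stopped too. This softens the point but does not remove it. Blinding prevents staff from choosing by arm; it does not prevent the infusion from causing more symptoms in one arm.
- **Some data would survive in the chart,** since nurses record bowel function and adverse reactions as routine care. But study VAS scores are recorded by research staff, and the plan does not say that they continue after removal.
- **A missing discharge score cannot enter a Wilcoxon test without imputation.** True. The valid criticism is that such patients may also be lost from every other analysis.

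**Conclusion.** The concern holds and should be fixed before analysis. The stated rules remove patients from the primary comparison for an event that the study drug can cause, and no analysis restores the randomised groups. The direction and size of any bias cannot be fixed from the documents. On the assumed cases it runs from nothing, through 0.09 to 0.26 points at correlation 0.5 (type I error about 5% to 7%), to 0.52 points (about 13%) at the extreme. These figures rest on normal scores with SD 2 and one to three lidocaine exclusions, with none or one in the placebo arm.

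The case for change rests on principle more than on demonstrated magnitude: the rule governs the primary test in a trial of 46 patients, and the loss may be irreversible if follow-up ends at removal. The bias claim applies mainly to the stopped-infusion rule; aborts and conversions are chiefly a matter of precision.

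**What to change.** 1. **Primary set:** all randomised patients whose study infusion (lidocaine or saline) was started, analysed as randomised, whether or not it was later stopped or failed. This is a modified as-randomised set and should be named as such. It is defensible because a never-started infusion precedes any study drug and clinical staff are blinded.
2. **Replacement:** only for patients whose infusion never started. Report all replacements and exclusions by arm and reason.
3. **Follow-up:** continue VAS, opioid and safety data collection after a stop unless consent is withdrawn.
4. **Missing scores:** state which missing score triggers the removal rule. Keep patients lacking only the discharge score in the GEE, secondary and safety analyses, and add a multiple-imputation sensitivity analysis for the primary score.
5. **Aborts and conversions:** analyse as randomised, with a sensitivity analysis omitting them. Once converted patients are included, state how placebo patients started on lidocaine, and any unblinded scores, are handled.
6. **Present exclusions:** keep as a per-protocol sensitivity analysis.
7. **Reconcile** the Intervention, Outcome Assessment and Removal sections on who is removed or replaced, and on whether a stopped saline infusion counts.

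No rule for when an infusion is stopped changes.

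**Cost.** Wording, follow-up of a few more patients, and possibly a larger sample because of dilution. For 80% power with normal scores and a fixed number of stops:

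- One stop: 20 analysed per arm, so 46 enrolled as now.
- Three stops: 24 per arm; 24/0.9 = 26.7, so 27 per arm and 54 enrolled.
- Three stops and one crossover: 26 per arm; 26/0.9 = 28.9, so 29 per arm and 58 enrolled.

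These are lower figures. On the conservative efficiency of 0.864 that reproduces the plan's own sample size, one stop gives about 77% at 20 per arm and needs 22 (22/0.9 = 24.4, so 25 per arm and 50 enrolled), and three stops give about 78% at 24. If stops grow with sample size, four among 24 give about 76–77% even with normal scores.

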This is a prospective, randomized, double-blinded, placebo-controlled clinical trial on lidocaine infusion for pain control and opioid consumption in patients undergoing either robotic-assisted laparoscopic prostatectomy or robotic-assisted laparoscopic partial nephrectomy at University of Missouri Hospital. Patients will be randomized in a 1:1 fashion and stratified by the type of surgery to receive a perioperative intravenous 0.8% lidocaine infusion at 1 mg/kg/h if $<$ age 65 and 0.5 mg/kg/h if \geq age 65 or an equal volume and rate of normal saline as a placebo. The infusion will be started 15 minutes after endotracheal intubation and continue for 24 hours.

After obtaining written consent, subjects will be randomized to receive lidocaine or normal saline. The anesthesiologist, surgeon, nurses, research staff, and patient will be blinded to the intervention. Masked infusion bags of 0.8% lidocaine or normal saline will be prepared by the investigational pharmacy at University of Missouri Hospital. To avoid any compromise in the blinding process, the investigational pharmacist will enter "Study Medication" in the medical record.

Perioperative care, surgery and anesthesia, for all subjects will be per standard hospital protocol.

In short:

Upon arrival to the operating room, patients will be placed supine on the operating table and intravenous (IV) lines connected to allow initiation of IV lidocaine or saline following anesthetic induction. IV antibiotics will be utilized if clinical necessary based on the discretion of the anesthesiologist and attending surgeon. Standard perioperative monitoring including a

continuous electrocardiogram, pulse oximetry, urine output, non-invasive arterial pressure measurement, end-tidal CO₂ and temperature will be utilized. Intravenous fluid use during surgery will be provided by the anesthesiology team as clinically indicated. Anesthesia will be standardized. Induction will be with lidocaine 1.5 mg/kg, fentanyl 1 mcg/kg, propofol 1.5 to 2 mg/kg, and rocuronium 0.6 mg/kg. Patient will then be prepared and draped in sterile fashion. Timeout will be performed.

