Patient may go to the floor or ICU with the infusion. Orders will be included in surgeon's post-operative orders including the stop time at 24 hours. The infusion pump will be programmed using Guardrails settings, it will be on separate infusion pump from IV fluids with sign for pump - local toxicity, obtained from anesthesia pain nurse.

Patients will be monitored clinically for toxicities during the postoperative period. Per standard of care the nurse caring for the patient will be required to document any adverse events to lidocaine every four hours and anesthesiology pain nurses will monitor these reports. If patients experience the presence of perioral paresthesia, metallic taste, tinnitus, confusion, agitation,

muscle spasms, and seizures, the lidocaine infusion will be stopped and a lidocaine toxicity protocol will start by the standard of care. The subject will be removed from the study.

At initial follow-up appointment, patient will be asked to bring in prescribed opioids, if applicable, to determine how much was required in their outpatient recovery. Pill count will be done and compared to distributed quantity. VAS score will be also assessed.

THERAPEUTIC AND DIAGNOSTIC AGENTS

Lidocaine is the intravenous analgesic. Lidocaine infusion will be stored and dispensed by the Investigational Pharmacy at University Hospital. A 0.8% Lidocaine infusion will be injected intravenously using an administration set with a filter at a constant rate of 1 mg/kg/h for ages < 65 and 0.5 mg/kg/h for ages ≥ 65. Patients with BMI ≥ 40 will be dosed using ideal body weight.

RECRUITMENT PLAN

Patients will be recruited from the practices of the Division of Urology, Department of Surgery. The study will be introduced to every eligible patient scheduled for robot assisted laparoscopic prostatectomy and robot assisted laparoscopic partial nephrectomy by the participating consenting physicians from the Department of Surgery-Urology Division and a written consent obtained prior to surgery by the consenting research personnel. Candidate subjects will be provided time to consider the study, to read the informed consent document at their convenience, and discuss the study with family and others, as desired.

PRETREATMENT EVALUATION

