Various symptoms including perioral paresthesia, metallic taste, tinnitus, confusion, agitation, muscle spasms, and seizures have been described when the plasma lidocaine was higher than 5 $\mu\text{g}/\text{mL}$. While under general anesthesia, evidence of toxicity may be evident through bradycardia, increased intervals and widening QRS complex and may be increased with hypercapnia.¹⁶ However, it has been shown to be more cardio-protective, rather than cardio-toxic in prospective randomized study³⁶. The toxic levels of lidocaine are unlikely to be experienced at the levels used in our protocol. Our study is using the low end of the recommended dose and rate of 1-2 mg/kg/h. We additionally are utilizing a bolus only as a part of routine anesthesia induction, which is recommended to be 1-2 mg/kg and start the infusion 15 minutes after the endotracheal intubation.

Signs of lidocaine toxicity will be monitored per University Hospital standard of care protocol. This includes assessment and documentation by floor nursing staff, every 4 hours, of the signs and symptoms of lidocaine toxicity. The presence or lack of toxicity is reported in the medical record at these time points and pain nurse with the Department of Anesthesiology and Perioperative Medicine review this information. Management and review of medications will also be performed by the surgical and inpatient care teams per standard of care. Toxicity in our study will be evaluated clinically postoperatively by the presence of perioral paresthesia, metallic taste, tinnitus, confusion, agitation, muscle spasms, and seizures. Following standard of care, if there is concern of possible toxicity a lidocaine level may be ordered per standard of care.

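### Subjects stopped for suspected toxicity leave both the study and the analysis with no safety exception, so a toxicity summary of the analysed set would show no such stops

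*Combined protocol and SAP*

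**What the plan says.** Three statements in the combined protocol and SAP bear on this.

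- Overview of Study Designation, Intervention: after a list of seven clinical signs ending in "muscle spasms, and seizures, the lidocaine infusion will be stopped and a lidocaine toxicity protocol will start by the standard of care", the next sentence reads "The subject will be removed from the study". No severity threshold is given.
- Toxicities/Side Effects: the same seven signs are the study's definition of toxicity: "Toxicity in our study will be evaluated clinically postoperatively by the presence of perioral paresthesia, metallic taste, tinnitus, confusion, agitation, muscle spasms, and seizures".
- Criteria for Removal from Study: "If lidocaine infusion is stopped subject will be excluded from analysis". The neighbouring sentences exclude subjects converted to open surgery and subjects with no primary-endpoint data.

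No safety population is defined. The secondary endpoints include no toxicity measure. Biostatistics describes pain analyses only; it mentions further analyses without saying what they are or whom they include.

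Safety events are recorded in other ways. Signs are charted through "assessment and documentation by floor nursing staff, every 4 hours" and reviewed by the pain nurses. Complications are graded under the "institutional standard for complications reporting for all surgical patients", including medication complications. Serious adverse events go to the IRB within 5 calendar days.

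**The concern.** During the infusion, the event that defines toxicity is also the event that takes the subject out of the study and out of the analysis. If the trial later reports tolerability by arm in the subjects it analysed, stops for suspected toxicity will be absent from both arms because of the rule, and not because none occurred. A zero obtained that way would seem to support the protocol's expectation, under Benefits and Risks, that adverse outcomes will not arise at these doses, while carrying no information about it.

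The count is needed in both arms. The Design section says "The anesthesiologist, surgeon, nurses, research staff, and patient will be blinded to the intervention", so a non-specific sign such as confusion or agitation can stop a saline infusion too. Only the two counts together show whether lidocaine adds anything, and the analysed set supplies neither.

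**Working it through.** **Inputs.** The arm size comes from Sample Size and Table 2: 20 per arm with 10% dropout. 20 / (1 − 0.10) = 22.2, rounded up to 23, which reproduces the stated enrolment of 23 per arm. The stop rate p is not given anywhere, so 1%, 2%, 5% and 10% are assumed. Toxicities/Side Effects calls toxic levels unlikely, which favours the lower end.

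**Step 1: the rule.** A toxicity stop leads to removal (Intervention) and to exclusion from analysis (Criteria for Removal from Study). The number of toxicity stops in the analysed set is therefore 0 in each arm for every p. This needs no assumed rate. It covers stops only: a sign that appears after the 24-hour infusion has ended, or that does not lead to a stop, is unaffected.

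**Step 2: how often it would matter.** With 23 subjects started on lidocaine, expected stops = 23p and the chance of no stop = (1 − p)^23.

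| Assumed p | Expected stops | Chance of no stop | Stops in analysed set |
|---|---|---|---|
| 1% | 0.23 | 79% | 0 |
| 2% | 0.46 | 63% | 0 |
| 5% | 1.15 | 31% | 0 |
| 10% | 2.30 | 9% | 0 |

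**Step 3: what a reader would see.** Intervals are exact two-sided 95% (Clopper-Pearson). For zero events in m subjects the upper limit is 1 − 0.025^(1/m). One and two stops are used because they are near the expected numbers at 5% and 10%.

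| Stops among 23 | All started | Analysed set, no replacement |
|---|---|---|
| 1 | 4.3% (0.1% to 21.9%) | 0 of 22, upper limit 15.4% |
| 2 | 8.7% (1.1% to 28.0%) | 0 of 21, upper limit 16.1% |

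Criteria for Therapeutic Response/Outcome Assessment replaces subjects whose infusion fails. The text does not say that this covers a deliberate stop for toxicity. If it did, the analysed set would show 0 of 23 (upper limit 14.8%) against 1 of 24 (4.2%, 0.1% to 21.1%) or 2 of 25 (8.0%, 1.0% to 26.0%).

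**Step 4: the arm comparison.** With both arms at zero by rule, the displayed difference is zero whatever happened. Restoring the subjects would not make the comparison powerful: even 3 of 23 against 1 of 23, a purely illustrative split, differs by 8.7 percentage points with a two-sided Fisher p of 0.61. The table would be descriptive.

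**The case against.** The strongest reply is that the exclusion was meant for efficacy. It stands beside the primary-endpoint rule, the only analyses described are of pain, and the safety sections carry no such exclusion. That may well be the intent. But the sentence refers to analysis without qualification, the Intervention section removes the subject from the study altogether, and no safety set is named. If efficacy-only is meant, the fix just writes it down.

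A second reply is that nothing planned is distorted: there is no toxicity endpoint and no toxicity table. This stands, and it limits the point. Changing the exclusion sentence alone would produce no safety count, so the table has to be added as well.

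A third is that the information can be recovered. It can: the signs are charted, the reason for each exclusion could be tabulated, and the randomisation table gives the arm. The document commits to none of this by arm. It also refers to institutional data and safety monitoring plans that are not reproduced, so the absence of a by-arm summary is established for this document only.

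Two stronger inferences are tempting and should be resisted. One is that toxicity events are lost or go unreported. They do not: charting, complication grading and serious adverse event reporting continue regardless of the analysis set. The other is that, because the sentence names the lidocaine infusion, only lidocaine subjects are excluded and the arms are treated differently. Staff are blinded and the removal rule is applied at the bedside, so in practice it falls on both arms. The wording would matter only if exclusions were decided after unblinding.

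**Conclusion.** The point holds, and it is minor. As written, subjects stopped for a listed toxicity sign are removed and excluded with no safety exception, so a by-arm toxicity summary on the analysed set would show zero such stops at any true rate and could not fairly describe tolerability. No specified safety analysis is biased, because none is specified, and detection and reporting of events are intact. How the same exclusion affects the pain comparison is a separate question, not judged here.

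The zero itself rests only on the text. Its practical size rests on assumed stop rates: quite possibly nil at 1% to 2% (79% to 63% chance of no stop among 23 on lidocaine), and 1.2 to 2.3 dropped stops expected at 5% to 10%. The counts would remain too small for a test.

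**What to change.** In Intervention, Criteria for Therapeutic Response/Outcome Assessment and Criteria for Removal from Study, state that removal, replacement or exclusion for a stopped infusion or for open conversion does not apply to safety reporting. This should not be worded so as to endorse the exclusion for efficacy. Write 'study infusion' in place of 'lidocaine infusion' in the stopping and exclusion rules.

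Add one descriptive table to Biostatistics, for example: *All randomised subjects in whom the study infusion was started will be summarised by randomised arm, including those stopped, converted or replaced, with the number and percentage who had a listed toxicity sign and who had the infusion stopped for suspected toxicity. Events after the start of any open-label lidocaine will be listed separately.* The last sentence is needed because lidocaine may be started after open conversion in a subject who was on saline.

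The cost is a few sentences, one table and a little more abstraction. Most of the data are in the floor nursing record. A stop during surgery would have to come from the anaesthesia record, since "While under general anesthesia, evidence of toxicity may be evident through bradycardia, increased intervals and widening QRS complex". There are no new visits, and the decision to stop an infusion does not change. The downside is a possibly less favourable toxicity rate, with wide intervals.
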